The length of time for individual HSCT-TMA patient participation in Stage 2 (if he or she does not continue to Stage 3) was approximately 14 to 18 weeks, depending on the time from screening to the first dose of OMS721 administration. Follow-up visits for patients who do not continue to Stage 3 will occur on Day 29, Day 36, Day 50, and Day 92.

Patients with HSCT-TMA who have completed the Stage 2 treatment period may be eligible for an additional 4 weeks of treatment if the Investigator believes the patient is at risk for relapse of TMA or has not responded to the initial 4 weeks of treatment, the patient tolerated OMS721 treatment, and the patient has no conditions that increase the risk of OMS721 treatment (e.g., serious active infection). The patient's treating Investigator and the Sponsor's medical monitor will determine eligibility for Stage 3 based upon the patient's response to therapy and safety and tolerability prior to the last scheduled treatment visit in Stage 2 in order to determine the appropriate PK draws following that visit. Patients entering Stage 3 will not undergo the Follow-up visits in Stage 2.

Figure 5: Stage 3 Study Design Schematic (HSCT-TMA Cohort)

The **Stage 3** study schedule for the HSCT-TMA cohort (Cohort 5) includes 8 visits across 2 periods:

Period 2 (continued from Stage 2)- Treatment (Visit T-5 to Visit T-8, 4 weeks)

Period 3 -Follow-up (Visit F-1 to Visit F-4, 6 weeks)

Follow-up visits in Stage 3 for the HSCT-TMA cohort will occur on Day 57, Day 64, Day 78, and Day 92. The length of time for individual TTP/HSCT-TMA patient participation in Stage 3 will be approximately 10 weeks, and the total length of time in Stage 2 and Stage 3 will be approximately 14 to 18 weeks.

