12.3. Reporting Adverse Events

12.3.1. Adverse Event Reporting

Adverse events will be collected from the time informed consent is obtained until the last Follow-up visit.

All AEs will be documented in the source records and will be recorded in the CRFs as appropriate. All AEs, whether observed by the Investigator or reported by the patient, and whether or not thought to be related to the study drug, will be recorded on the appropriate CRF. In describing AEs on the CRF, standard, medically accepted terminology will be used.

The description of each AE will identify the date of onset, duration, severity (see Section 12.2.2 for Definitions of Severity), any action taken (including any diagnostic procedures or laboratory tests performed and all treatments that were administered), the outcome of the event, and relationship to the study drug.

Any medical condition that is present at the time that the patient is screened should be considered as baseline and not recorded as an AE. However, if the medical condition increases in frequency or severity during or following administration of the study drug, it will be recorded as an AE on the appropriate CRF.

An AE is defined as any untoward medical occurrence in a patient administered a pharmaceutical product and which does not necessarily have to have a causal relationship with this treatment. Adverse events may be reported by the patient, discovered by the Investigator and Investigator's staff, or detected through physical examination, laboratory test, or other means.

Adverse events include:

- Any unfavorable and unintended sign, medical diagnosis, or symptom that occurs between the time of the first administration of study drug and the study duration required by the protocol.
- Any new undesirable medical experience or an unfavorable and unintended change of an existing condition that occurs between the time of the first administration of study drug and the study duration required by the protocol, whether or not considered related to study drug.
- Abnormal laboratory findings considered by the Investigator to be clinically significant, i.e., those that are unusual for the population being studied or individual patient.

Whenever possible, the Investigator should group signs or symptoms that constitute a single diagnosis into a single event term. For example, cough, rhinitis, and sneezing might be grouped together as *upper respiratory tract infection*.

CONFIDENTIAL

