3.4. Analysis of Safety Endpoints

3.4.1. Clinical Adverse Events

Adverse events collected during the study and significant AEs will be combined for analysis. They will be labeled as adverse events for simplicity. Significant AEs are the AEs that occurred outside the protocol-specified reporting period and will be collected for the HSCT-TMA patients only. For reporting purposes, AEs will be divided into 2 categories:

1. Those that occurred prior to the start of study treatment (pre-treatment events) and
2. Those that occur or worsen in intensity after the start of study treatment (treatment-emergent adverse events).

Summary of AEs will include the non-serious AEs during the AE evaluation period and all reported serious AEs. The AE evaluation period is defined from the time of informed consent to 37 days after the last study drug administration.

All AEs will be classified by system organ class and preferred term using the Medical Dictionary for Regulatory Activities (MedDRA). An AE is considered treatment related if the relationship to study drug is either probable or possible as assessed by the investigator.

Patient incidence of the following AEs will be provided:

- Pre-treatment AEs by MedDRA System Organ Class (SOC), preferred term, dose and disease
- Treatment-emergent AEs by MedDRA SOC, preferred term, dose and disease
- Treatment-emergent AEs by MedDRA preferred term, dose and disease
- Treatment-related AEs by MedDRA SOC, preferred term, dose and disease
- Treatment-emergent AEs by MedDRA preferred term, maximum severity, dose and disease
- AEs leading to study discontinuation by MedDRA SOC, preferred term, dose and disease
- Treatment-emergent serious AEs (SAEs) by MedDRA SOC, preferred term, dose and disease
- Treatment-related SAEs by MedDRA SOC, preferred term, dose and disease
- AEs leading to death by MedDRA SOC, preferred term, dose and disease

In addition, the following analyses will be performed:

- Treatment-emergent AEs and treatment-emergent SAEs during the AE evaluation period will be summarized separately for patients with and without anti-drug antibody postdose.
- Treatment-emergent AEs that started or worsen in intensity after the AE evaluation period will be summarized with patient incidence by SOC, preferred term, disease group and dose level.
- Pre-treatment and treatment-emergent significant infections will be summarized by infection type which will be determined before database lock and will be documented in the CSR.

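### Non-serious AEs that start or worsen more than 37 days after the last dose get no relatedness or severity table, and for HSCT-TMA their only incidence table also holds chart-collected events

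*SAP*

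**What the plan says.** SAP 3.4.1 and Protocol 13.2.9.2 give the same rule. The scope is set first: "Summary of AEs will include the non-serious AEs during the AE evaluation period and all reported serious AEs". The window follows: "The AE evaluation period is defined from the time of informed consent to 37 days after the last study drug administration". The list of incidence tables comes next and includes the treatment-related and maximum-severity tables. Treatment-emergent AEs that begin or get worse after the window have one table of their own, in which they "will be summarized with patient incidence by SOC, preferred term, disease group and dose level". That table has no relatedness or grade dimension. SAP 3.4.1 also promises listings of every AE and a summary of significant infections.

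Collection runs longer than the window. Protocol 12.3.1 states: "Adverse events will be collected from the time informed consent is obtained until the last Follow-up visit". The items recorded for each AE include severity, "the outcome of the event, and relationship to the study drug". The longest schedule is for HSCT-TMA/TTP patients treated in Stage 2 only, where Protocol 7.1.2 states: "Follow-up visits for patients who do not continue to Stage 3 will occur on Day 29, Day 36, Day 50, and Day 92". Their last scheduled dose is on Day 22.

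On pooling, SAP 3.4.1 states: "Adverse events collected during the study and significant AEs will be combined for analysis". It also says: "Significant AEs are the AEs that occurred outside the protocol-specified reporting period". These are gathered for HSCT-TMA only. Under Protocol 19.4, Table 2, they are dated events that led to a hospital stay or needed treatment. They come from medical records for up to 104 weeks after first dose, ending earlier at last contact or at the data cutoff.

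**The concern.** The investigator records a grade and a causality judgement for every prospective AE, and the tables built to show those two attributes stop before collection does. A non-serious Grade 3 event, or one judged related, that starts on day 40 after the last dose would be missing from both tables although the data exist. Safety is a co-primary endpoint, and SAP 2.8.5 says the interim report is meant to support a submission.

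For HSCT-TMA, the one table that does hold these events mixes two ascertainment rules under one label: all AEs up to the last visit, then only the more consequential ones from charts. A reader of that table cannot tell which rule produced a given incidence. The aHUS and TTP columns contain no chart component, so the disease columns are not like for like.

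**Working it through.** **Inputs.** Dose and visit days are from Protocol 7.1.1, 7.1.2, 10.1.1 and Appendices 19.1 to 19.3. Patient counts are from SAP Table 1. The window is 37 days.

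**Formulas.** Follow-up = last visit day − last dose day. Tail = follow-up − 37. The plan's stated follow-up lengths (8, 10 and 6 weeks) reproduce.

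| Schedule | Last dose | Last visit | Follow-up (days) | Stated (weeks) | Tail (days) | Tail / follow-up |
|---|---|---|---|---|---|---|
| Stage 1 | 22 | 78 | 56 | 8 | 19 | 34% |
| HSCT-TMA/TTP, Stage 2 only | 22 | 92 | 70 | 10 | 33 | 47% |
| HSCT-TMA/TTP, Stage 3 | 50 | 92 | 42 | 6 | 5 | 12% |
| aHUS, Stage 2 only | 78 | 120 | 42 | 6 | 5 | 12% |
| aHUS, Stage 3 | 162 | 204 | 42 | 6 | 5 | 12% |

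**What the last visit covers.** The visit before the last is 28 days after the last dose in every schedule (for example 50 − 22 = 28 and 78 − 50 = 28). The tail is therefore 5/14 (36%), 19/28 (68%) or 33/42 (79%) of the interval for which the last visit collects events.

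**Departures from nominal.** With visit windows, the Stage 1 tail runs from (78 − 7) − (22 + 1) − 37 = 11 days to (78 + 7) − (22 − 1) − 37 = 27 days. A Cohort 5 patient who stops after dose 1, 2 or 3 and keeps the Stage 2 visits has a tail of 92 − 1 − 37 = 54, 92 − 8 − 37 = 47 or 92 − 15 − 37 = 40 days.

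**Patient-days in the tail**, assuming all scheduled doses and full follow-up:
- Stage 1: (3 + 3 + 4) = 10 patients × 19 = 190.
- Cohort 4: (14 + 4) = 18 × 5 = 90.
- Cohort 5: (4 + 22 + 4) = 30 patients. 30 × 5 = 150 if all entered Stage 3; 30 × 33 = 990 if none did.
- All 58 patients: 190 + 90 + 150 = 430, to 190 + 90 + 990 = 1,270.
- The 28 HSCT-TMA patients: 2 × 19 = 38, plus 26 × 5 = 130 or 26 × 33 = 858. This gives 168 to 896.

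Stage 3 uptake is not given, so no point within these ranges can be chosen. Patient-days are not events, and the event count cannot be derived from the documents.

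**The case against.** **The rule is prespecified and consistent.** The two documents agree, and collecting for longer than the main summary window is a legitimate choice with a stated place for later events. This stands. It is why the window need not change, but it does not explain why the later table omits two attributes that were recorded.

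**The affected set is narrow.** SAEs at any time stay in the main tables, and an event that began inside the window stays in the relatedness and severity tables. Only non-serious events that newly start or worsen in the tail are affected. This stands.

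**The upper patient-day figures are extreme.** They need zero Stage 3 uptake and no death or dropout, in a disease that Protocol 5.1.2.3 describes as having a poor prognosis. This stands. They are bounds, not estimates.

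**The pooling is disclosed and incomplete.** Chart events that required inpatient hospitalization meet the SAE definition in Protocol 12.2.1, so they would also enter the main tables. Dates in the listings can separate the sources. Protocol Table 2 asks for dates and does not mention relatedness or severity for chart events, but the CRF is not visible, so whether those were captured is unknown. All of this stands, yet the table itself still mixes the two rules.

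**The tables will be sparse.** With 58 patients, a listing may serve nearly as well. This is fair, and it limits the weight of the point.

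A reader might infer that 37 days is too short for the drug, because Protocol 7.1 plans at least six weeks of follow-up for elimination. The documents do not support that. The sentence sets the length of visits, not an attribution window, and the readable text does not show how much drug remains on these days. Moreover, 37 days equals the treatment-period end in SAP 2.4 (last dose + 7) plus 30, although neither document gives this as the reason.

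**Conclusion.** The point holds as a cheap improvement. As written, relatedness and grade are recorded but not tabulated for non-serious AEs that start or worsen in the final 5, 19 or 33 nominal days before the last visit. For HSCT-TMA, the one incidence table holding all these events also contains chart-collected ones. Some infections may appear in the significant-infection summary as well.

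This rests on reading the scope sentence as governing the table list that follows it. That is the natural reading, and the existence of a separate later table supports it. The day counts assume nominal visit days and no later supplemental dose.

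A reader might infer that late AEs go unreported or that the co-primary safety assessment is unsound. Neither follows: the events are tabulated by term and listed, SAEs are fully covered, and SAP 2.8.4 makes safety descriptive, so no test or threshold depends on the cut.

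**What to change.** Keep the 37-day window. In SAP 3.4.1 and Protocol 13.2.9.2, replace the single later table with two:

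- (a) Prospectively collected treatment-emergent AEs from day 38 after the last dose to the last follow-up visit, by system organ class and preferred term within disease and dose, with treatment-related and maximum-severity tabulations.
- (b) Chart-collected significant AEs after the last follow-up visit, HSCT-TMA only, by system organ class and preferred term within dose.

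The SAP's own definition of significant AEs supplies the dividing date, because the protocol's reporting period ends at the last follow-up visit. The cost is one bullet in each document and minor programming, with no new data. The downside is a few extra sparse tables.

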10.1.2.5. Stage 2 and Stage 3 Treatment – Visit T-N (where N is > 1 [the week of treatment after the week of the first dose])

The following procedures will be performed on the subsequent doses of OMS721:

1. AEs, presence of TMA symptoms, concomitant medications, and therapies will be recorded.
2. Vital signs will be taken, including BP, pulse rate, RR, and temperature (after at least 5 minutes of rest in the supine position) at the following time points: prior to dosing and at 15 minutes, 30 minutes, 1 hour, and 2.5 hours after start of dosing.
3. Clinical laboratory tests will be performed for hematology, chemistry, LDH, haptoglobin, coagulation, and urinalysis (prior to OMS721 administration).
4. Blood sample for future research related to TMA will be taken (prior to OMS721 administration).
5. Serum PK samples will be taken at the following time points: prior to dosing and at 2 hours after end of dosing. At the last treatment visit, additional PK samples will also be taken at the following timepoints: 24 hours, 48 hours, and 72 hours after the end of the last dose.
6. Serum PD samples will be taken at the following time points: prior to dosing and at 2 hours after end of dosing.
7. OMS721 will be administered by IV infusion over approximately 30 minutes.
8. AEs during and after the IV infusion will be recorded.

10.1.2.6. Stage 2 or Stage 3 Follow-Up – Visit F-N (where N is the number of the follow-up visit)

The following procedures will be performed:

1. AEs, presence of TMA symptoms, concomitant medications, and therapies will be recorded.
2. Clinical laboratory tests will be performed for hematology, chemistry, LDH, and haptoglobin.
3. Blood sample for future research related to TMA will be taken.
4. Serum PK sample will be taken.
5. Serum PD sample will be taken.
6. Serum ADA sample will be taken.
7. Serum or urine pregnancy test will be performed in women of childbearing potential at the last Follow-Up visit only.

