13.2.9.2. Adverse Events

Adverse events collected during the study and significant AEs will be combined for analysis. They will be labeled as AEs for simplicity. Significant AEs are the AEs that occurred outside the protocol-specified reporting period and will be collected for the HSCT-TMA patients only. For reporting purposes, AEs will be divided into 2 categories:

- Those that occurred prior to the start of study treatment (pre-treatment events) and
- Those that occur or worsen in intensity after the start of study treatment (treatment-emergent adverse events).

Summary of AEs will include the non-serious AEs during the AE evaluation period and all reported serious AEs. The AE evaluation period is defined from the time of informed consent to 37 days after the last study drug administration.

All AEs will be classified by system organ class and preferred term using the Medical Dictionary for Regulatory Activities (MedDRA). An AE is considered treatment-related if the relationship to study drug is either probable or possible as assessed by the Investigator.

Patient incidence of the following AEs will be provided:

- Pre-treatment AEs by MedDRA System Organ Class (SOC), preferred term, dose, and disease
- Treatment-emergent AEs by MedDRA SOC, preferred term, dose, and disease

CONFIDENTIAL

No use, disclosure or reproduction outside of Omeros without prior written authorization

- Treatment-emergent AEs by MedDRA preferred term, dose, and disease
- Treatment-related AEs by MedDRA SOC, preferred term, dose, and disease
- Treatment-emergent AEs by MedDRA preferred term, maximum severity, dose, and disease
- AEs leading to study discontinuation by MedDRA SOC, preferred term, dose, and disease
- Treatment-emergent serious AEs (SAEs) by MedDRA SOC, preferred term, dose, and disease
- Treatment-related SAEs by MedDRA SOC, preferred term, dose, and disease
- AEs leading to death by MedDRA SOC, preferred term, dose, and disease

In addition, the following analyses will be performed:

- Treatment-emergent AEs and treatment-emergent SAEs during the AE evaluation period will be summarized separately for patients with and without ADA postdose.
- Treatment-emergent AEs that started or worsen in intensity after the AE evaluation period will be summarized with patient incidence by SOC, preferred term, disease group, and dose level.

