2.2. Analysis Populations

Efficacy analyses will be performed for the Full Analysis Set (FAS) population and the Per-protocol Patient Set (PAS) population. The FAS population will include all HSCT-TMA patients

who received any amount of study drug. The PAS population will include all HSCT-TMA patients who received at least 4 weeks of study treatment (treatment period is greater than or equal to 28 days).

Safety analyses will be based on the Safety Analysis Set population, which includes all patients (aHUS, TTP, and HSCT-TMA) who received any amount of study drug.

The Enrolled population is defined as all patients who completed the informed consent.

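### The adverse-event table by post-dose anti-drug antibody status ignores when the antibody appeared, so early death alone can make antibodies look protective and events before detection are counted under 'with'

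*SAP*

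**What the plan says.** SAP 3.4.1 plans one safety comparison by immunogenicity: "Treatment-emergent AEs and treatment-emergent SAEs during the AE evaluation period will be summarized separately for patients with and without anti-drug antibody postdose". Protocol 13.2.9.2 has the same rule: events "will be summarized separately for patients with and without ADA postdose". The grouping is therefore by patient, on any post-dose result.

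An event qualifies by its timing against the first dose only: "Those that occur or worsen in intensity after the start of study treatment (treatment-emergent adverse events" category in SAP 3.4.1. The window is also fixed without reference to ADA: "The AE evaluation period is defined from the time of informed consent to 37 days after the last study drug administration".

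ADA sampling runs to the last follow-up visit. For TTP/HSCT-TMA Stage 2, protocol 7.1.2 says: "Follow-up visits for patients who do not continue to Stage 3 will occur on Day 29, Day 36, Day 50, and Day 92".

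Unlike most of the other AE summaries in SAP 3.4.1, this bullet does not mention disease or dose. The safety population is the one "which includes all patients (aHUS, TTP, and HSCT-TMA) who received any amount of study drug" (SAP 2.2). SAP 3.3 refers the immunogenicity analysis to Section 2.8.3, which is blacked out in the public copy.

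**The concern.** ADA status develops during follow-up. If it is treated as a fixed label, two things happen.

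- **Survival selection.** A patient enters the with-ADA group only by living to a positive sample. A patient who dies early after negative samples is in the without group on the plain wording. Deaths then concentrate in the without group even if ADA has no effect.
- **Events before detection.** Everything since the first dose is counted under with ADA, including events that preceded the first positive sample.

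Safety is a co-primary objective and immunogenicity a secondary one. The visible integrated ADA analysis (protocol 13.2.7) covers effects on PK and PD, not adverse events. This is therefore the only visible table that sets safety against ADA, in a study whose interim report is meant to support a regulatory submission (SAP 2.8.5). A reader could take a reassuring contrast from it that is an artefact of who lived long enough to be tested.

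**Working it through.** The plan gives no figure for this split, so there is none to reproduce.

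**Step 1: AE window against last ADA sample.** Inputs are the dosing and sampling days in protocol 19.1 to 19.3. Window end = last scheduled dose day + 37.

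| Schedule | Last dose | Window end | Last ADA sample | Gap (days) |
|---|---|---|---|---|
| Stage 1 | 22 | 59 | 78 | 19 |
| TTP/HSCT-TMA Stage 2 | 22 | 59 | 92 | 33 |
| TTP/HSCT-TMA Stage 3 | 50 | 87 | 92 | 5 |
| aHUS Stage 2 | 78 | 115 | 120 | 5 |
| aHUS Stage 3 | 162 | 199 | 204 | 5 |

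In every schedule a patient first positive at the last sample has 100% of counted events before detection. In TTP/HSCT-TMA Stage 2, a first positive on Day 29 puts 28 of 59 window days (47%) before detection, and one on Day 50 puts 49 of 59 (83%). These are nominal days; visit slippage or supplemental doses could close a 5-day gap.

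**Step 2: effect of early death when ADA does nothing.** Schedule: TTP/HSCT-TMA Stage 2, samples at t = 8, 15, 22, 29, 36, 50, 92, window to Day 59. Assumptions, none from the documents:

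- 20% of patients seroconvert, at a time uniform on 0 to U, with U = 92 or U = 29.
- Death has a constant hazard, with p = 20% or 40% dead by Day 92, so S(t) = (1 − p)^(t/92).

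Let w_k be the share of seroconversions falling between sample k − 1 and sample k. Then:

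- P(positive) = 0.2 × Σ w_k S(t_k)
- P(positive and dead by Day 59) = 0.2 × Σ w_k [S(t_k) − S(59)], over samples before Day 59
- P(dead by Day 59) = 1 − S(59)
- The negative group is the remainder.

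Worked case, p = 20%, U = 92. The weights are 8, 7, 7, 7, 7, 14 and 42, each over 92. P(positive) = 0.174. P(positive and dead by Day 59) = 0.0070. P(dead by Day 59) = 1 − 0.8667 = 0.1333. Fatal event among positives = 0.0070/0.174 = 4.0%. Among negatives = (0.1333 − 0.0070)/(1 − 0.174) = 15.3%.

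| Seroconversion | Dead by Day 92 | Fatal, with ADA | Fatal, without ADA | Without ADA, unsampled excluded |
|---|---|---|---|---|
| Uniform to Day 92 | 20% | 4.0% | 15.3% | 13.3% |
| Uniform to Day 92 | 40% | 9.7% | 31.1% | 27.4% |
| By Day 29 | 20% | 9.5% | 14.3% | 12.2% |
| By Day 29 | 40% | 20.4% | 29.6% | 25.7% |

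The last column removes patients who die before the Day 8 sample (1.9% or 4.3%). The gap narrows but remains.

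**Step 3: effect of events before detection.** With a constant event rate while alive, the share of counted events in ADA-positive patients that precede detection is A/(A + B). Here A = Σ w_k S(t_k) min(t_k, 59), and B = Σ w_k [S(t_k) − S(59)]/λ over samples before Day 59, with λ = −ln(1 − p)/92. The result is 70% to 71% for U = 92 and 32% to 33% for U = 29.

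If nobody dies and seroconversion is unrelated to events, both groups have the same event incidence whatever this share is. Early detection of events misattributes them, but does not by itself create a difference between groups.

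**Step 4: does dating by first positive sample remove the artefact?** Under the same null, the death hazard is λ both before and after the first positive sample. Rates per patient-time therefore agree in the two states.

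**The case against.** The strongest reply is that the plan makes no causal claim. SAP 2.8.4 calls all safety analyses descriptive, the study is uncontrolled, ADA incidence is summarized by time (protocol 13.2.7), all AEs are listed, and events starting after the window have their own summary. That stands and limits the weight of the point. It does not correct the table: the listings let a reader check timing case by case, and the post-window summary is not split by ADA.

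Three stronger readings are tempting, and the documents do not support them.

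- **Patients with no post-dose sample are classed as without ADA.** No visible text says so. SAP 2.8.3 is blacked out and may contain the rule, so this cannot be called an omission. The point does not need it, as the last column in Step 2 shows.
- **Events before detection create a false harmful or protective signal.** Step 3 shows they do not alone. They blur attribution and dilute a real effect; differential early death produces the false contrast.
- **The percentages estimate the bias in this trial.** They do not. They come from the schedule with the widest gap and depend heavily on seroconversion timing. The assumed death rates may be high, because exclusion 8 removes patients with life expectancy under 3 months. In SAP Table 1, 30 of 58 patients have aHUS or TTP (25 + 5), and no aHUS schedule was worked through.

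**Conclusion.** The point holds as a limited one. Following the rule exactly gives a table in which survival to sampling decides group membership and the order of ADA and event is ignored. The date comparison needs only the nominal schedules. The fatal-event contrast, 4% to 20% with ADA against 14% to 31% without when ADA has no effect, rests on assumed seroconversion and death rates. Within each scenario the gap runs from about 5 to 21 percentage points, always in the direction of apparent protection. It would shrink with fewer early deaths or earlier seroconversion.

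This is one descriptive table. The primary efficacy rule is unaffected, so the case for change is that a better table is cheap, not that a main conclusion is at risk.

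**What to change.** In SAP 3.4.1, with protocol 13.2.9.2 kept in line:

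- Classify each treatment-emergent AE and SAE by onset before, or on or after, the first ADA-positive post-dose sample. Every patient starts in the before state.
- Use patient-time in each state as the denominator.
- Show patients with no post-dose ADA sample as a separate group.
- Present the table by disease.
- Keep any ever/never split only as a listing, with ADA sample dates beside AE dates.

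Extending the AE cut to the last visit is not a substitute: a patient first positive there would still contribute almost no positive time.

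One related item must be reconciled. The Stage 2 and 3 schedule tables (protocol 19.2 and 19.3) show an ADA sample at each dosing visit, but the list in protocol 10.1.2.5 ("The following procedures will be performed on the subsequent doses of OMS721") contains none. On that list alone, the first post-dose sample for TTP/HSCT-TMA Stage 2 would be Day 29.

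The cost is one reprogrammed table from dates already collected. The limits should be stated beside it. Positive time will be sparse: at an assumed 20%, 0.2 × 28 = 5.6 HSCT-TMA patients would seroconvert. Onset is known only to the sampling interval, which is 42 days between Day 50 and Day 92. The table remains descriptive.
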